9.2 Relationship of Adverse Event to Study Drug

The investigator or designated physician-sub investigator responsible for the care of the subjects in the study will assess the relationship of each AE or laboratory abnormality to FWD1802 using clinical judgement and the following considerations:

- No: Evidence exists that the AE has an etiology other than the FWD1802. For SAEs, an alternative causality must be provided (eg, pre-existing condition, underlying disease, intercurrent illness, or concomitant medication).
- Yes: There is reasonable possibility that the event may have been caused by the study drug.

It should be emphasized that ineffective treatment should not be considered as causally related in the context of AE reporting.

The relationship to study procedures (eg, blood draw) should be assessed using the following considerations:

- No: Evidence exists that the adverse event has an etiology other than the study procedure.

- Yes: There is reasonable possibility that the adverse event occurred as a result of protocol procedures.

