¹Including more severe injection site related sciatica, neuralgia, neuropathic pain, and peripheral neuropathy.

In the pooled safety population (N=1127) from clinical trials comparing FASLODEX 500 mg to FASLODEX 250 mg, post-baseline increases of ≥1 CTC grade in either AST, ALT, or alkaline phosphatase were observed in >15% of patients receiving FASLODEX. Grade 3-4 increases were observed in 1-2% of patients. The incidence and severity of increased hepatic enzymes (ALT, AST, ALP) did not differ between the 250 mg and the 500 mg FASLODEX arms.

Combination Therapy with Palbociclib (PALOMA-3)(FDA, 2021)

The safety of FASLODEX 500 mg plus palbociclib 125 mg/day versus FASLODEX plus placebo was evaluated in PALOMA-3. The data described below reflect exposure to FASLODEX plus palbociclib in 345 out of 517 patients with HR-positive, HER2-negative advanced or metastatic breast cancer who received at least 1 dose of treatment in PALOMA-3. The median duration of treatment for FASLODEX plus palbociclib was 10.8

months while the median duration of treatment for FASLODEX plus placebo arm was 4.8 months.

Permanent discontinuation associated with an adverse reaction occurred in 19 of 345 (6%) patients receiving FASLODEX plus palbociclib, and in 6 of 172 (3%) patients receiving FASLODEX plus placebo. Adverse reactions leading to discontinuation for those patients receiving FASLODEX plus palbociclib included fatigue (0.6%), infections (0.6%), and thrombocytopenia (0.6%).

The most common adverse reactions ($\geq 10\%$) of any grade reported in patients in the FASLODEX plus palbociclib arm by descending frequency were neutropenia, leukopenia, infections, fatigue, nausea, anemia, stomatitis, diarrhea, thrombocytopenia, vomiting, alopecia, rash, decreased appetite, and pyrexia.

The most frequently reported Grade ≥ 3 adverse reactions ($\geq 5\%$) in patients receiving FASLODEX plus palbociclib in descending frequency were neutropenia and leukopenia.

Adverse reactions ($\geq 10\%$) reported in patients who received FASLODEX plus palbociclib or FASLODEX plus placebo in PALOMA-3 are listed in Table 6, and laboratory abnormalities are listed in Table 7.

Table 6 Adverse Reactions ($\geq 10\%$) in PALOMA-3

Adverse Reactions	FASLODEX plus Palbociclib N=345			FASLODEX plus Placebo N=172		
	All Grades	Grade 3	Grade 4	All Grades	Grade 3	Grade 4
	%	%	%	%	%	%
Infections and Infestations						
Infections ¹	472	3	1	31	3	0
Blood and Lymphatic System Disorders						

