4.6 Definitions of Dose-Limiting Toxicity (DLT)

All AEs of the specified grades should count as DLTs except those that are clearly and incontrovertibly due to disease progression or extraneous causes.

1. Hematological toxicity:

- CTCAE Grade ≥ 4 thrombocytopenia;
- CTCAE Grade 4 neutropenia lasting >7 days;
- CTCAE Grade ≥ 3 febrile neutropenia, where Grade 3 febrile neutropenia is defined as ANC $<1000/\text{mm}^3$ and a single temperature of $>38.3^\circ \text{C}$ (101°F) or a sustained temperature of $\geq 38^\circ \text{C}$ (100°F) for more than one hour;
- CTCAE Grade 3 thrombocytopenia ($\geq 25,000/\text{mm}^3$ and $<50,000/\text{mm}^3$) associated with bleeding;
- CTCAE Grade 4 ($<25,000/\text{m}^3$) thrombocytopenia lasting >5 days;

2. Non-hematological toxicity:

- Hy's law, defined as:
 - ✧ AST or ALT > 3 x the upper limit of normal (ULN) AND
 - ✧ Total bilirubin > 2 x ULN AND
 - ✧ Alkaline phosphatase < 2 x ULN AND

- ◇ No other reason for liver injury
- ALT or AST >8x ULN, ALT or AST >5x ULN for more than 2 weeks, ALT or AST >3x ULN and (TBL >2x ULN or INR >1.5)
 - ◇ For patients with hepatic metastases, AST or ALT > 8 x ULN or AST or ALT > 5 x ULN for \geq 14 days
- Grade > 3 non-hematologic toxicity with the exception of the following
 - ◇ Grade 3+ fatigue \geq 7 days regardless of baseline Grade;
 - ◇ Grade 3 nausea and vomiting, lasting \leq 2 days with optimal medical management;
 - ◇ Grade 3 diarrhea lasting \leq 3 days with optimal medical management
 - ◇ \geq 3+ non-hematologic abnormalities should also include laboratory values that cause symptoms.

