6.7 Concomitant Medications

Concomitant Medications means any drug other than the study drug used during the study period (including the screening period and all study visits).

If the use of the combination medications is due to an adverse event, it must be documented and reported in accordance with the relevant regulations and the adverse events and serious adverse events requirements of Section 9 of this protocol.

The supervisor must be notified if the use of the combination medications affects the subject's participation in the study.

Details of all drug combinations must be recorded, including drug name, reason for use, start date, end date or continuation date, indication, and dosage.

The use of other antitumor treatments or experimental drugs is prohibited during the study period. Palliative radiotherapy and bisphosphonate therapy for bone lesions are permitted. Herbal preparations or related over-the-counter preparations containing herbal ingredients are prohibited during the study and treatment period (For details please see Appendix 5).

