10.5.1 Adverse Events

Clinical and laboratory adverse events will be coded using the Medical Dictionary for Regulatory Activities (MedDRA). System Organ Class (SOC), Preferred Terminology (PT), will be attached to the clinical database. See Section 9 for the definition and the severity of AE.

Events will be summarized on the basis of the date of onset for the event. A treatment-emergent adverse event (TEAE) will be defined as following:

- Any AEs with an onset date on or after the study drug start date and no later than 30 days after permanent discontinuation of study drug.
- Any AEs leading to premature discontinuation of study drug.

Summaries (number and percentage of subjects) of TEAEs by SOC and PT will be provided. TEAEs will also be summarized by relationship to study drug and severity. In addition, TEAEs leading to premature discontinuation of study drug and study will be summarized and listed.

All AEs collected during the course of the study will be presented in data listing with a field for treatment-emergent event (yes/no).

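### Protocol section 9.2 judges AE causality against FWD1802 alone, so Part B's summary of related TEAEs can leave out toxicity that belongs to the palbociclib combination

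*Protocol*

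**What the plan says.** The primary objectives (Protocol section 2 and synopsis) cover RP2D/MTD, safety and tolerability, both for FWD1802 alone and for FWD1802 with palbociclib. Part B is the combination part.

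Section 9.2 has one question on drug causality. The investigator "will assess the relationship of each AE or laboratory abnormality to FWD1802 using clinical judgement". The two answers are:

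- "No: Evidence exists that the AE has an etiology other than the FWD1802". For SAEs an alternative cause must be named, with these examples: "eg, pre-existing condition, underlying disease, intercurrent illness, or concomitant medication".
- The affirmative answer reads: "Yes: There is reasonable possibility that the event may have been caused by the study drug".

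Section 10.5.1 uses the answer: "TEAEs will also be summarized by relationship to study drug and severity".

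On what palbociclib is, the document is uneven. Section 6.7 states: "Concomitant Medications means any drug other than the study drug used during the study period". The synopsis lists palbociclib as a combination product beside the test product, and Table 2 gives it a row of its own, apart from concomitant medications.

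DLTs have a separate rule. Section 4.6 and the synopsis count every AE of a listed grade, "except those that are clearly and incontrovertibly due to disease progression or extraneous causes". For Part B the synopsis sets the evaluation period as the first cycle of the combination.

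**The concern.** When two drugs are given together and the pair is under test, a causality question about only one of them does not describe the pair. Section 1.4.1 gives investigators a ready alternative explanation: in the cited trial the most frequent grade 3 or higher reactions "in patients receiving FASLODEX plus palbociclib in descending frequency were neutropenia and leukopenia". A site asked only about FWD1802 has documented reason to attribute neutropenia in Part B to palbociclib and answer No.

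The Part B table of related TEAEs would then describe FWD1802 given alongside palbociclib, not the regimen whose tolerability is being judged. If FWD1802 were making a palbociclib effect worse, the familiar pattern would be the one most easily set aside. An attribution that was never collected cannot be rebuilt at the analysis stage, so this cannot be left to the SAP.

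A second, smaller matter is that the DLT exception for extraneous causes does not say how a palbociclib effect is to be treated in Part B.

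**Working it through.** **Step 1: what section 9.2 allows in Part B.** Take an event for which there is evidence of a palbociclib cause.

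| Test in 9.2 | Is it met? |
|---|---|
| No: evidence of a cause other than FWD1802 | Yes, on the wording |
| Yes: reasonable possibility that the study drug caused it | Depends on the investigator's view of FWD1802 |

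The two tests are not mutually exclusive, and 9.2 does not say which prevails when both are met. No is therefore permitted, but not required. No section asks for relationship to palbociclib or to the combination.

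**Step 2: how much toxicity is open to this.** Inputs are from Table 6 (fulvestrant plus palbociclib, N = 345; fulvestrant plus placebo, N = 172), the text below it, and the Part B size in section 5.1 and Table 13.

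- Grade 3-4 neutropenia with palbociclib: 55% + 11% = 66%.
- Grade 3-4 neutropenia with placebo: 1% + 0% = 1%.
- Share of the palbociclib-arm rate that exceeds the placebo rate: (66 - 1)/66 = 98%.
- Expected patients in Part B at that rate: 12 x 0.66 = 7.9.

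Section 4.2.2 gives about 24 subjects for Part B instead of 12. With 24 the expected number would be 24 x 0.66 = 15.8. The proportion is unchanged.

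These rates cover all treatment, with a median of 10.8 months on fulvestrant plus palbociclib (section 1.4.1). They indicate what a relatedness table over the whole of Part B might omit, and say nothing specific about cycle 1.

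**Step 3: how much of this could be a DLT.** Under section 4.6 neutropenia is a DLT only if it is grade 4 lasting more than 7 days, or febrile. At the cited rates, in 12 patients:

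- Grade 3: 12 x 0.55 = 6.6 patients, not a DLT without fever.
- Grade 4 of any duration, over all treatment: 12 x 0.11 = 1.3 patients, before applying the duration condition and the 28-day window.
- Febrile neutropenia (0.9%): 12 x 0.009 = 0.1 patients.

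Most of the neutropenia in step 2 therefore never reaches the DLT rule.

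**Step 4: when inconsistent DLT counting would matter.** The synopsis applies the 3+3 rule to Part B, and section 4.4 sets it out. For a genuine DLT, counting or excusing it changes the outcome at one of three (expand, against escalate at none of three) and at two of six (stop, against escalate at one of six). At one of six it changes nothing, because one of six already escalates.

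**Step 5: what is kept whatever the attribution.** Sections 9.4.1 and 9.5.1 require AEs to be recorded and reported regardless of relationship. Section 10.5.1 tabulates TEAEs by SOC and PT and by severity, and section 10.5.3 summarises DLTs by dose level. Only the split by relationship depends on the 9.2 answer.

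**The case against.** The strongest reply is that little is lost. All AEs are recorded, the incidence and severity tables for Part B describe the combination in full, and the escalation rule in section 4.4 does not use the relatedness code. A Yes needs only a reasonable possibility. Section 1.2.2 reports that FWD1802 inhibits CYP3A and P-gp, and section 9.1.1 lists effects of a suspected interaction as AEs, so an investigator who suspects an interaction can answer Yes. No passage calls palbociclib a concomitant medication. The CRF is not shown and may already carry a palbociclib field.

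Most of this is right, and it limits the point to the relatedness summary. It does not close the gap. Section 9.1.1 governs what is recorded, not how it is attributed, and the protocol requires no judgement on palbociclib or the combination, whatever a CRF may contain.

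Three stronger readings are tempting and are not supported:

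- A reader might infer that palbociclib-type events will be coded as unrelated. Section 9.2 makes that likely, but does not prescribe it.
- A reader might infer that a No under 9.2 removes an event from the DLT count. Section 4.6 does not refer to the 9.2 answer, counts events by default and sets a much higher bar for excusing them. The Part B window is also defined on the combination.
- A reader might infer that excusing any grade 4 neutropenia changes an escalation decision. Grade 4 lasting 7 days or less without fever is not a DLT, and even a true DLT alters the decision only in the configurations of step 4.

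**Conclusion.** The point holds for attribution. Followed as written, section 9.2 cannot yield a Part B summary of TEAEs related to the combination, although the combination's tolerability is a primary objective. The toxicity most exposed is neutropenia: 66% against 1% at grade 3-4 in the cited trial, or about 8 of 12 patients. That figure assumes FWD1802 plus palbociclib resembles fulvestrant plus palbociclib over a similar treatment time. It is the number of patients with events open to a No, not a forecast of how many will receive one. Total incidence and severity remain intact.

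On DLTs the finding is narrower. The phrase on extraneous causes is undefined for Part B, and the document does not treat palbociclib uniformly, so two sites could handle the same event differently. The documents give no basis for estimating how often this would happen.

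**What to change.** In section 9.2, for Part B, record relationship separately to FWD1802, to palbociclib and to the combination, and carry this into the AE form. In section 10.5.1, summarise Part B TEAEs related to either drug as well as those related to FWD1802. This should be in place before Part B enrols.

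Separately, the sponsor should reconcile section 4.6 and the matching synopsis text with section 6.7, the synopsis entry for the combination product and Table 2, so that sites treat palbociclib effects consistently when counting Part B DLTs. How they should be counted is a clinical decision for the sponsor and the SMC, and no rule is proposed here.

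The cost is an added causality field on the Part B AE form, short edits to the sections named, and a higher reported rate of related events in Part B. No sample size changes.

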9.3 Method of Detecting AEs and SAEs

Care will be taken not to introduce bias when detecting AEs and/or SAEs. Open-ended and non-leading verbal questioning of the subject is the preferred method to inquire about AE occurrence. Subjects are also required to report any AEs and/SAEs, including but not limited to loose stools or diarrhea.

9.4 Recording AEs and SAEs

9.4.1 All Adverse Events Regardless of Seriousness

Any adverse medical condition or laboratory abnormality with an onset date before initial dose of study drug administration is considered to be pre-existing in nature. Any known pre-existing conditions that are ongoing at time of study entry, and any events of Grade 3 or 4 severity that occur up to 14 days before study entry (even if resolved prior to study entry) should be recorded in the appropriate section of the CRF.

All AEs occurring from initial FWD1802 administration up to 30 days following the last dose of FWD1802 must be recorded as an AE in the subject's source documents and on the CRF regardless of frequency, severity (grade) or assessed relationship to the study drug.

In addition to new events, any increase in the frequency or severity (i.e., toxicity grade) of a pre-existing condition that occurs after the subject begins taking FWD1802 is also considered an AE.

9.4.2 Clinical Laboratory Abnormalities and Other Abnormal Assessments as Adverse Events and Serious Adverse Events

Abnormal laboratory findings (e.g., clinical chemistry and hematology) or other abnormal assessments (e.g., ECGs) that are judged by the investigator as clinically significant will be recorded as AEs or SAEs if they meet the definitions as defined in Section 9 Assessments of Adverse Events. Clinically significant abnormal laboratory findings or other abnormal assessments that are detected during the study or are present at baseline and significantly worsen following the start of the study will be reported as AEs or SAEs. However, clinically significant abnormal laboratory findings or other abnormal assessments that are associated with the disease being studied, unless judged by the investigator as more severe than expected for the subject's condition, or that are present or detected at the start of the study and do not worsen, will not be reported as AEs or SAEs. The investigator will exercise his or her medical and scientific judgment in deciding whether an abnormal laboratory finding or other abnormal assessment is clinically significant.

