8. Eastern Cooperative Oncology Group (ECOG) performance status of 0 or 1.
9. At least one measurable lesion according to RECISTv1.1 criteria.
10. Life expectancy ≥ 12 weeks.
11. Adequate organ and bone marrow function (no use of hematopoietic stimulating factor, no blood transfusion or human albumin within 7 days prior to screening):
- Blood routine: Absolute neutrophil count (ANC) $\geq 1.5 \times 10^9/L$; Platelet count (PLT) $\geq 100 \times 10^9/L$; Hemoglobin (HGB) ≥ 90 g/L;
 - Liver function: Serum Total bilirubin (TBIL) ≤ 1.5 Upper limit of normal value (ULN); Alanine aminotransferase (ALT) and Aspartate transferase (AST) $\leq 3 \times ULN$ in subjects without liver metastasis; ALT or AST $\leq 5 \times ULN$ with liver metastasis;
 - Renal function: Serum creatinine $\leq 1.5 \times ULN$ or estimated creatinine clearance (CLcr) ≥ 60 mL/min as calculated using Cockcroft-Gault formula;
 - Coagulation function: Activated Partial thromboplastin Time (APTT) and international normalized ratio (INR) $\leq 1.5 \times ULN$ (or within target range if on anticoagulation therapy);
 - Cardiac function: Echocardiography (ECHO) shows left ventricular ejection fraction (LVEF) $> 50\%$.
12. Women of childbearing potential must have a negative serum pregnancy test within 7 days prior to the first dose. Female patients of childbearing potential must agree to use effective methods of contraception from the time of signature of informed consent, throughout the study and for 6 months after the last dose of the investigational product, like double barrier methods, condoms, oral or injectable contraceptives, intrauterine devices, etc. All female subjects will be considered to be of childbearing potential

unless they are postmenopausal, postmenopausal, or sterilized (hysterectomy, tubal resection).

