9.1.1 Adverse Event Definition

An AE is any untoward medical occurrence in a subject or clinical investigation participant administered a pharmaceutical product and which does not necessarily have a causal relationship with this treatment. An AE can therefore be any unfavorable and unintended sign (including an abnormal laboratory finding), symptom, or disease temporally associated with the use of a medicinal (investigational) product, whether or not related to the medicinal (investigational) product.

Examples of an AE include:

- Significant or unexpected worsening or exacerbation of the condition/indication under study.
- Exacerbation of a chronic or intermittent pre-existing condition including either an increase in frequency and/or intensity (grade) of the condition.
- New conditions detected or diagnosed after investigational product administration even though may have been present prior to the start of the study.
- Signs, symptoms, or the clinical sequelae associated with a suspected interaction of the investigational product with a concomitant medication.

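### Section 9.4.2 exempts disease-associated laboratory findings from AE recording on a looser test than Section 4.6 uses for DLTs, and no text says which rule governs a laboratory value that meets a DLT criterion

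*Protocol*

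**What the plan says.** **Section 9.4.2 (laboratory abnormalities as AEs)** works in three steps.
- Abnormal findings "that are judged by the investigator as clinically significant will be recorded as AEs or SAEs" if they also meet the Section 9 definitions.
- Clinically significant findings that arise on study, or that were there at baseline and worsen significantly, are reported.
- A sentence opening with a contrast then removes two groups, which "will not be reported as AEs or SAEs". One is findings "associated with the disease being studied, unless judged by the investigator as more severe than expected" for that patient. The other is findings present at the start that do not worsen.

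**Section 4.6 (DLT definition, with the same counting rule in the synopsis)**: "All AEs of the specified grades should count as DLTs except those that are clearly and incontrovertibly due to disease progression or extraneous causes". Several criteria are laboratory values: platelets, neutrophils, ALT/AST, bilirubin and INR. One addresses liver metastases directly: "For patients with hepatic metastases, AST or ALT > 8 x ULN or AST or ALT > 5 x ULN for" at least 14 days.

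**Sections 9.1.1 and 9.4.1** point the other way. The AE definition covers unfavourable signs "including an abnormal laboratory finding", whether or not drug-related. Section 9.4.1 also treats "any increase in the frequency or severity (i.e., toxicity grade) of a pre-existing condition" after dosing starts as an AE.

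**Section 5.2** admits patients with liver metastases at ALT or AST up to 5 x ULN. **Section 7.3.1** puts all clinical laboratory results on the CRF, and **Section 10.5.3** lists DLT assessments and laboratory tests by subject.

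**The concern.** The two tests differ in strength and in order. Section 9.4.2 asks whether a finding is associated with the cancer and no worse than the investigator expected. Section 4.6 asks whether it is beyond dispute due to progression or an extraneous cause. Because Section 4.6 counts AEs, the weaker test comes first, and a value it removes need never meet the stronger one.

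Establishing the RP2D and/or MTD is a primary objective (Section 2), and Section 4.5 defines the MTD by DLT incidence. The trial is open-label and first-in-human, with cohorts of three to six after the first dose level, so a single event can decide whether the dose rises. The TEAE summaries in Section 10.5.1 would carry the same omission. Sites could also classify the same value differently, depending on whether they follow Section 9.4.1 or 9.4.2.

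**Working it through.** **1. Does the exemption reach a DLT criterion?** Take a patient with liver metastases who enters with ALT close to 5 x ULN, as Section 5.2 allows. On treatment ALT stays modestly above 5 x ULN for three weeks.
- Section 4.6: the hepatic-metastasis criterion is met. It is a DLT unless the strict exemption applies.
- Section 9.4.1: it is an AE if the toxicity grade has risen.
- Section 9.4.2, second step: reportable if the worsening is significant.
- Section 9.4.2, exemption: not reportable if judged disease-associated and not more severe than expected. This limb is not restricted to findings that failed to worsen; that condition belongs to the other limb.

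The sections therefore give different answers for one value, and none states precedence. The same could be argued for platelets, neutrophils or INR, but the protocol gives less reason to expect those to be attributed to the disease.

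**2. What does one missed event do?** From Section 4.4:
- 2 DLTs in 6 = 33.3%: stop. Recorded as 1 in 6 = 16.7%: escalate.
- 1 DLT in the first 3: enrol 3 more. Recorded as 0 in 3: escalate at once.

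Every miss moves towards escalation.

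**3. Illustration of size.** The protocol states no figure to reproduce. Let p be the true DLT rate and m the share of true DLTs not recorded. The protocol gives no m, so the values below are assumptions. With p' = p(1 − m), Section 4.4 gives

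P(escalate) = (1 − p')³ + 3p'(1 − p')² × (1 − p')³ = (1 − p')³ + 3p'(1 − p')⁵

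For p = 0.33, near the Section 4.5 limit:
- m = 0: p' = 0.33; 0.67³ + 3(0.33)(0.67⁵) = 0.301 + 0.134 = 0.434
- m = 0.10: p' = 0.297; 0.347 + 0.153 = 0.500
- m = 0.25: p' = 0.2475; 0.426 + 0.179 = 0.605
- m = 0.50: p' = 0.165; 0.582 + 0.201 = 0.783

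At higher true rates:

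| True DLT rate | m = 0 | m = 0.10 | m = 0.25 | m = 0.50 |
|---|---|---|---|---|
| 0.40 | 0.309 | 0.378 | 0.494 | 0.709 |
| 0.50 | 0.172 | 0.234 | 0.351 | 0.600 |

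These are probabilities for one cohort. They are not probabilities of selecting a given MTD, because Section 4.5 also requires six patients at that dose.

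**The case against.** The best defence is that the protocol, taken as a whole, leans towards recording. Section 9.1.1 counts abnormal laboratory findings as AEs whatever the cause, Section 9.4.1 captures grade increases, and Section 9.4.2 itself says significant worsening is reported. In the liver-metastasis example, a value above 5 x ULN exceeds the entry limit, so it is a worsening if screening met that limit. The laboratory DLT criteria are mostly numeric, all results are on the CRF and listed, and the SMC decides each step after the DLT period is complete. One can also say that the specific DLT section naturally governs DLT assessment, leaving Section 9.4.2 for routine AE entry.

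Much of this stands, and it rules out several stronger readings that a reader might infer:
- *That the protocol plainly permits laboratory DLTs to be dropped.* It contradicts itself; it does not grant clear permission.
- *That Section 4.6 excuses only progression.* It also excuses extraneous causes, though on the same strict standard, so the gap in strength remains.
- *That DLTs will be lost at a known rate, or the MTD raised by a known amount.* Nothing in the protocol gives m. The mechanism touches only laboratory DLTs judged disease-associated, so m is the fraction of DLTs of that kind times the chance that each goes unrecorded.
- *That the DLT count is the designated primary endpoint.* Section 3 labels no endpoint primary; DLT incidence is a listed safety endpoint that feeds the primary objective.

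The defence does not close the gap. The rule on recording AEs regardless of relationship presupposes that the value is an AE. The contrasting sentence in Section 9.4.2 qualifies the reporting rule before it. No text tells anyone to compare raw laboratory values with Section 4.6, or says that a qualifying value counts without an AE record.

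**Conclusion.** The conflict is real and should be resolved, in this limited form: Section 9.4.2 contradicts Section 9.4.1 and applies a looser attribution test ahead of the one in Section 4.6. On a literal reading, a laboratory value that meets a DLT criterion can therefore escape DLT assessment. Whether that would happen, and how often, cannot be settled from the protocol.

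The direction is certain: a miss can only favour escalation. The size is illustrative. At a true DLT rate of 33%, the chance that one cohort escalates runs from 43% with no loss to 50%, 61% and 78% for assumed losses of 10%, 25% and 50% of all DLTs. The calculation assumes independent patients and the Section 4.4 rule applied as written.

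This cannot be left to a statistical analysis plan, because it governs what sites record.

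**What to change.** Add one sentence, cross-referenced in Sections 4.6, 9.4.1 and 9.4.2. It should say that every laboratory value meeting a Section 4.6 criterion during the DLT period is recorded and put to the SMC for DLT assessment, whether or not Section 9.4.2 would make it an AE. It should also state which attribution standard governs that assessment; the choice is for the sponsor and investigators, but it must be a single one. In the same edit, reconcile the disease-association exemption in Section 9.4.2 with the toxicity-grade rule in Section 9.4.1.

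No DLT threshold, dose or escalation rule changes. The cost is a short protocol amendment and a few additional records.
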